#### Covariates:

• Negative life events

This measure assesses exposure to 31 possible negative life events and assesses if they occurred before age 18, after age 18 or in the past year. Seven additional adverse childhood experiences will also be specifically assessed.

- Interpersonal Violence Short Form/Revised Conflicts Tactics -Short form
  This twenty-item measure is designed to capture intimate partner
  violence. Specifically, it assesses three tactics used when there is
  conflict in the relationships of dating, cohabiting, or marital couples:
  Negotiation, Physical Assault, and Psychological Aggression.
  Questions are answered in terms of frequency of occurrence.
  Scoring can occur in a variety of ways as outlined here
- Demographics

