# Section 3 – Data analytic plan

• *Power analysis*. Sample size was estimated using G\*Power and standard guidelines for testing mediation,  with α=.05, β=.80, and the standard deviation bound at ±1.91. Effect size estimates were derived from prior research on SC interventions for PTSD, which found a small-medium effect size (Cohen's d=0.2-0.5).  Particularly since the effect of MSC to reduce PTSD symptoms is emerging research, findings have been mixed regarding effect sizes for direct and indirect effects of SC interventions on PTSD, with some studies finding large effects of reduced PTSD due to SC interventions,  and others finding medium effect sizes.  (Of note, few randomized trials have been conducted).  To account for additional covariates, the clustering design,  and Type 1 error due to multiple tests, a small-medium effect size of .3 was conservatively estimated. Sample size appropriate for mediation was derived from a percentile bootstrap method, which simulations consistently show to be the most powerful test compared to similar methods (e.g., Sobel, bias-corrected bootstrap).  This yielded a final sample size of 162. Based on the team's prior research, we conservatively estimate 80% retention over time for a target enrollment of 202, for a total of 8 cohorts of 24-26 participants (divided equally into two groups per cohort). In the

team's prior work, 82% of those screened were eligible for participation: thus, we will aim to screen 246 WEH.

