- Statistical analysis. Initial analysis will include descriptive statistics. Data will be screened for outliers and deviations from normality; results will be considered in subsequent analyses. Patterns of missing data will be examined using logistic regression (0=missing; 1=complete) and will be reported in results. Based on prior research, very little missing data on key independent or dependent variables is expected. Any missing data on independent variables or continuous dependent variables will be imputed using multiple imputation and related methods. Although cohorts should be comparable in terms of demographics (e.g., age, ethnicity) and other risk factors (e.g., type of drug use, history of recidivism), propensity score methods and/or multilevel analyses (with cohort/cluster as a random effect) will be utilized to account for these or any other covariates statistically different between cohorts at baseline. Reliability for computed scores will be assessed using Cronbach's alpha. Next, a series of t-tests and chi-squares will examine differences between groups (MSC vs. TAU). Then, for each dependent variable of interest, key predictors and covariates will be examined using a series of t-tests, chi-squares, and ordinary least squares (for continuous outcomes) and logistic (for dichotomous outcomes) bivariate regression models. Type, timing and amount of trauma exposure will be examined as covariates, given their link with PTSD incidence, severity,  substance use,  and distress.

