- To evaluate reductions in PTSD symptoms, first, treatment response ( $\geq$  5-point reduction in symptoms) and clinically meaningful improvement (≥ 10-point reduction in symptoms) will be calculated for both immediate and 4-month follow-up. Potential covariates (e.g., demographic indicators; type, timing and amount of trauma exposure, including history of incarceration) will be screened for inclusion (included if p<.05). Change over time will be analyzed, using data from the three time points, using a mixed-effects repeated measures approach. This will also allow for a test of fixed (e.g., treatment group) and random (e.g., cohort) effects over time and conserves power by capitalizing on the longitudinal design. Reductions in PTSD will be examined using a modified Poisson distribution with robust variance, which tends to be less biased than a logit-based approach. Reductions in symptoms (measured continuously) will also be evaluated using a Gaussian distribution. Substance use will be evaluated using the TLFB, quantified as time to first use, days of use and relapse status (abstinent [did not use], lapse [used after study intervention but did not revert to regular use], or relapse [used substances for more than one third of days]). 34,35 Group x time contrasts will be tested. Identical analytic approaches will be used to examine secondary outcomes (suicidality, depression, and anxiety).
- To test for mediation effects, AGReMA (A Guideline for Reporting Mediation Analyses of Randomized Trials and Observational Studies) will be followed. A series of longitudinal structural equation models (SEM) will examine both direct and indirect effects by which change in mediators (emotion regulation, trauma-related guilt, trauma-related shame, moral injury and craving) are associated with change in PTSD, substance use, and secondary outcomes over time. Confidence intervals for indirect effects will be obtained through percentile bootstrap. SEM has the capacity to test for bidirectional

effects between PTSD symptoms and substance use. Model fit (e.g., Root Mean Square Error of Approximation) will be compared to find hypothesized paths that best fit the data.

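### The covariate set is picked by p<.05 screening in the trial's own data instead of being fixed in advance, and baseline scores are not assured a place as covariates

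*Combined protocol and SAP*

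**What the plan says.** In Section 3 (Data analytic plan), the bullet on PTSD reductions gives the candidates as "Potential covariates (e.g., demographic indicators; type, timing and amount of trauma exposure, including history of incarceration" and says they "will be screened for inclusion (included if p<.05". The list is introduced by an e.g., so it is open. The bullet does not say what the p-value tests.

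The preceding bullet (Statistical analysis) supplies the likely meaning: "for each dependent variable of interest, key predictors and covariates will be examined using a series of t-tests, chi-squares, and ordinary least squares" and logistic bivariate regressions. The same bullet has a second route to adjustment. Propensity scores and/or multilevel methods are to account for demographics, risk factors and "any other covariates statistically different between cohorts at baseline".

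The PTSD analyses are a mixed-effects repeated-measures model on three time points with group-by-time contrasts, and a modified Poisson model for reductions in PTSD. Reductions are defined as falls of at least 5 and at least 10 PCL-5 points, at both follow-ups. Baseline PCL-5 is not named as a covariate in either model. Secondary outcomes follow the same approach.

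**The concern.** Two things are at stake, and they should be kept apart.

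The first is pre-specification. If adjustment is decided by tests on the trial's own outcome data, the adjusted model is known only after outcomes are seen, and it can differ between outcomes. The candidate pool is large. Subsection 2.7 says of the life-events instrument, "This measure assesses exposure to 31 possible negative life events", each placed in one or more of three periods, which gives 31 × 3 = 93 possible indicators before any summary score is formed. The trial is open-label (Subsection 2.1), so a fixed model is one of the few safeguards available.

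The second is precision. The covariate most likely to matter for a symptom score is its own baseline value. The plan collects it but does not assign it a role as a covariate.

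**Working it through.** **Inputs from the plan.** Section 3 states "This yielded a final sample size of 162" and "we conservatively estimate 80% retention over time for a target enrollment of 202". Check: 162/0.80 = 202.5 and 202 × 0.80 = 161.6, so 202 is reproduced to rounding. The planned effect is .3, taken here as a standardised mean difference. The plan gives no covariate–outcome correlation, no baseline–follow-up correlation and no intracluster correlation (ICC). Values of these below are assumptions.

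**1. What the screen keeps.** By Fisher's z, a covariate with true correlation ρ passes a two-sided .05 test with probability of about Φ(atanh(ρ)·√(n−3) − 1.96). With n=162, √159 = 12.61:

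| ρ | passes | dropped |
|---|---|---|
| .10 | 24% | 76% |
| .15 | 48% | 52% |
| .20 | 72% | 28% |
| .30 | 97% | 3% |

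For k independent pure-noise candidates, the chance that at least one enters is 1 − .95^k: 23% at k=5, 40% at k=10, 64% at k=20, 80% at k=31.

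**2. What the screen costs if applied mechanically.** Simulation with n=162, five covariates each with ρ=.15, no clustering, 10,000 trials:

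| | unadjusted | screened | fixed set |
|---|---|---|---|
| Type I error | .049 | .049 | .050 |
| Power at .3 | .48 | .49 | .51 |
| SD of estimate (power runs) | .157 | .151 | .150 |

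The screen shows no inflation and loses about 1 to 2 power points against the fixed set.

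**3. What the latitude could permit.** Null trials, n=162, no clustering, ten candidates of which three are prognostic at an assumed .2. Each single model held about 5%. Taking the best of three models (unadjusted, screened, or screened plus imbalanced covariates) gave about 7%. Also allowing a choice between change score and baseline adjustment gave about 10%. This bounds what an unfixed model allows and predicts nothing about conduct.

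**4. The baseline score in the continuous analysis.** Assume equal variances σ² at baseline and follow-up, correlation r, complete data and no clustering. In a three-time-point model with no constraint on baseline means, the group-by-time contrast at a follow-up is the difference in mean change.

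- Variance of a change: 2σ²(1−r).
- Residual variance after adjusting for baseline: σ²(1−r²).
- Ratio: 2(1−r)/[(1−r)(1+r)] = 2/(1+r).
- r=.5: 2/1.5 = 1.33, like losing 1 − 1/1.33 = 25% of the sample.
- r=.7: 2/1.7 = 1.18, like losing 15%.

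Power at 81 per arm and .3 SD is about Φ(.3/√(2v/81) − 1.96), where v is the variance above with σ=1:

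- r=.5: v = 1.00 gives .48; v = .75 gives .60.
- r=.7: v = .60 gives .69; v = .51 gives .76.

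Simulation agrees (.49 to .61, and .68 to .75).

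**5. The responder models.** Responder status is cut from baseline minus follow-up. Under the same assumptions that reduction correlates with baseline at (1−r)/√(2(1−r)) = √((1−r)/2), which is .50 at r=.5 and .39 at r=.7. Baseline PCL-5 is therefore related to the outcome by construction, yet it is not named for these models.

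**The case against.** The strongest reply is that the screen does almost no numerical harm. That stands: step 2 shows it, and no claim of Type I inflation or a sizeable power loss from the screen itself is supported. (Those runs ignore the eight cohorts.)

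It can also be said that the figures in step 4 concern how baseline is handled, and that deleting the p-value condition alone would leave them unchanged. That also stands. A baseline score with r=.5 would pass the screen almost surely, so the issue is that it is not on the named list and has no stated place in the model. The two matters belong together only because one fixed set containing the baseline value settles both.

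Several stronger readings are tempting, but the documents do not carry them:

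- A reader might infer that about half of modest predictors are lost. That holds only near ρ=.15. The range is 76% to 28% over ρ=.10 to .20, and the plan gives no such correlation.
- A reader might infer that the screen is the only way in. The baseline-difference rule is another, though it is data-driven too and its and/or leaves the method open.
- A reader might infer that every follow-up gets its own model. The mixed model uses all three time points together, so only the responder models could split by visit.
- A reader might set the likely arm imbalance in a baseline score, √(2(1+24.25·ICC)/101) = .17 to .21 SD at an assumed ICC of .02 to .05, against the .3 effect and call it bias. The group-by-time contrast subtracts the baseline difference, so that comparison does not measure bias in the planned analysis.

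**Conclusion.** The concern holds as a pre-specification and precision point. No adjustment set is fixed, and both stated routes to adjustment depend on trial data. That the screen runs against each outcome is an inference from the Statistical analysis bullet, since the screening sentence does not say so. The screen's own cost is about 1 to 2 power points with no Type I inflation; its harm is that the adjusted model is settled after outcomes are seen.

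The larger loss comes from leaving baseline out as a covariate: a variance ratio of 1.33 to 1.18 for r=.5 to .7, equivalent to 25% to 15% of the sample. This assumes unconstrained baseline means, which the plan does not specify either way, equal variances and no clustering. It is worth correcting, but it does not invalidate the trial.

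**What to change.** In Section 3:

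- Delete the p<.05 inclusion condition. Name one short covariate set before outcome data are seen, and keep it whatever its p-values turn out to be.
- Include the baseline value of the outcome wherever Subsection 2.7 lists a baseline measure: PCL-5, AUDIT, DAST, PROMIS anxiety, depression and loneliness, and Beck hopelessness. Further covariates are for the sponsor to choose.
- Adjust the continuous analyses for baseline, or constrain baseline means to be equal across arms in the repeated-measures model.
- Add baseline PCL-5 to the modified Poisson responder models.
- Keep cohort as a random effect, as already planned.
- Label screened or imbalance-driven models as sensitivity analyses.

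Some outcomes named in Section 3 have no baseline measure listed in Subsection 2.7: the TLFB outcomes (time to first use, days of use, relapse status) and suicidality. For these, use the fixed set without a baseline value.

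The cost is SAP wording and a few participant-level degrees of freedom. The baseline scores listed above are already collected.

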#### SECTION 1A. RESEARCH STUDY OVERVIEW

#### **Subsection 1A.1 Overview & Introduction**

This three-year study will be a mixed-method, open-label cluster randomized clinical trial to test the benefit of the adapted mindful self-compassion intervention (MSC) at improving primary (PTSD, substance use) and secondary outcomes (depression, anxiety, helplessness, loneliness) among a sample of women experiencing homelessness (WEH) with PTSD/SUD residing in a residential drug treatment site (RDTS). An exploratory aim will be to elucidate mechanisms of treatment-response and maintenance or remission of symptoms.

Phase 1 of this three-year study was completed in December 2023. In Phase 1, a Community Advisory Board (CAB) was created, with women from the RDTS as well as site staff (including clinicians and substance use counselors). The CAB and the UCLA research team jointly created a semi-structured interview guide that was used with four focus groups (total N=27) of trauma-exposed WEH living at the RDTS. The participants completed acceptability and feasibility questionnaires and provided feedback on program design and administration. These suggestions were brought to the CAB and together the study design was finalized accordingly.

Phase II of this study will begin in Winter/Spring 2024. This will be a clinical trial comparing the MSC intervention to treatment as usual (TAU).

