#### 3. Phase II Reimbursement

- a. Women will receive \$5 for the eligibility screener; \$15 for completing baseline measures; \$10 per session in the intervention; \$20 for the post-intervention follow-up and \$10 if they complete an additional interview; and \$30 for the 4-month follow-up.
  - i. Women are paid in cash or a Visa gift card and must sign on the iPad (via REDCap) that they have received the payment. If a virtual follow-up, the individual who provides compensation will sign. This must also be initiated, signed, and dated by the RA or GSR in charge of payment.

Subsection 2.3 - Phase II Recruitment & Treatment Overview

Table 3. O	Table 3. Overview of Phase II Assessments							
Intervention	Recruitment	Eligibility Screen	Baseline	Weekly	Post- Intervention Follow-up	4-Month Follow-up		

MSC	Info meetings with PI at RDTS	PTSD SBT a	Psychosocial questionnaires b,c,d Demographics Locator Guide e	Home practice adherence Accept & feasibility activities f	Psychosocial questionnaires b,c,d ~20-minute interview	Psychosocial questionnaire s b,c,d
TAU	Info meetings with PI at RDTS	PTSD SBT a	Psychosocial questionnaires b,c,d Demographics Locator Guide e	Short psych surveys g	Psycho-social questionnaires b,c,d	Psycho-social questionnaire s b,c,d

aPTSD, SBT=Short Blessed Test (cognitive impairment screen; >9=likely cognitive impairment); bPrimary (PTSD, substance use) & Secondary (anxiety, depression, hopelessness, loneliness) Outcomes, cMediators: emotion-regulation, self-compassion, moral injury, trauma-related guilt, trauma-related shame, craving, mindfulness; dCovariates: negative life events; cLocator Guide will be updated regularly; fUsed to provide detailed feedback on acceptability & feasibility of MSC intervention; gSurveys on attitudes, personality, other non-clinical factors. MSC=Mindful Self Compassion; TAU=Treatment as Usual

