#### **Assessments**

#### Primary outcomes:

• PTSD PCL-5 (lifetime, past year)

PTSD symptoms will be measured using the PTSD Checklist for DSM-5 (PCL-5),  $^{1,2}$  which will be scored continuously and according to diagnostic criteria. The PCL-5 initially starts with the identification of the presence of exposure to a DSM-V traumatic event; assesses actual or threatened death, serious injury or sexual violence; and whether the person directly experienced it. Twenty additional items assess all four B-E criteria (re-experiencing, avoidance, negative thoughts or cognitions, hyperarousal), assessed on a Likert-type scale from 0 (not at all) to 4 (extremely). Treatment response will be defined as a  $\geq$  5-point reduction in symptoms and clinically meaningful improvement as  $\geq$  10-point reduction in symptoms. PTSD will be assessed for worse lifetime event and (if applicable) worst event in the past year.

Alcohol Use Disorders Identification Test (AUDIT)
 The AUDIT is part of the National Institute on Drug Abuse (NIDA)
 Clinical Trials Network (CTN) Common Data Elements for use in

clinical trials. The Audit is a 10-item alcohol screen that helps identify persons who are hazardous drinkers or who have active alcohol use disorders. It can be calculated as a sum score and will be analyzed as a continuous and categorical (yes/no used alcohol) outcome.

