### • Drug Abuse Screening Test-10 item (DAST)

The AUDIT is part of the NIDA CTN Common Data Elements for use in clinical trials. The DAST is a 10-item brief, self-report instrument for population screening, clinical case finding and treatment evaluation research. It can be used with adults and older youth. The DAST-10 yields a quantitative index of the degree of consequences related to drug abuse. The instrument takes approximately 5 minutes to administer and may be given in either a self-report or interview format. The DAST may be used in a variety of settings to provide a quick index of drug abuse problems. It will be evaluated continuously and as a categorical outcome (yes/no).

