### Assessments (see detailed description above)

### Primary outcomes:

- PTSD PCL-5 (lifetime, past year):
- Substance use AUDIT DAST

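### Section 3 analyses the primary substance-use outcome with the TLFB, which is in neither instrument list; its quantities cannot be built from the listed AUDIT and DAST-10

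*Combined protocol and SAP*

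**What the plan says.** **Status of the outcome.** Subsection 1A.1 sets out "primary (PTSD, substance use) and secondary outcomes". Subsections 2.2 and 2.6 and the footnote to the assessment overview table in Subsection 2.3 ("Primary (PTSD, substance use) & Secondary (anxiety, depression, hopelessness, loneliness) Outcomes") also class substance use as primary.

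**Instruments.** Under its primary outcomes, Subsection 2.7 lists the PCL-5 for PTSD, then AUDIT and DAST-10. On AUDIT it says: "It can be calculated as a sum score and will be analyzed as a continuous and categorical (yes/no used alcohol) outcome". On DAST-10 it says "The DAST-10 yields a quantitative index of the degree of consequences related to drug abuse" and "It will be evaluated continuously and as a categorical outcome (yes/no". The post-assessment list in Subsection 2.10 reads "Substance use AUDIT DAST".

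**Analysis.** Section 3 says: "Substance use will be evaluated using the TLFB, quantified as time to first use, days of use and relapse status". The status has three levels: abstinent, lapse and relapse. Relapse is defined by use on over a third of days. Section 3 does not mention AUDIT or DAST-10.

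**The concern.** The measurement sections and the analysis section describe different measures for the same primary outcome. If the instrument lists are right, the stated primary analysis has no data to run on. If Section 3 is right, the lists omit a primary instrument.

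Either way, a reader cannot tell which result will count as the trial's test of substance use. That choice would be left until data exist, in an open-label trial, among several codings of AUDIT and DAST-10 or several TLFB quantities. No coding or quantity is ranked first, and no primary time point is named.

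**Working it through.** The plan gives no figure to reproduce. The check is a comparison of texts, followed by a test of whether one measure can be derived from the other.

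**Step 1: where the TLFB appears.**
- Section 3, statistical analysis: once, unexpanded.
- Acronym list: absent.
- Subsection 2.7, baseline battery: absent.
- Subsection 2.10, post-assessment list: absent.
- Subsection 2.2, post-intervention visit: repeats the baseline measures, so adds nothing.
- Subsections 2.2 and 2.12, 4-month visit: outcomes are re-assessed, with no further instrument named.
- Weekly TAU surveys: attitudes, personality and other non-clinical topics, so no record of use.

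**Step 2: what each Section 3 quantity needs, and what the listed instruments supply as described.**

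| Section 3 quantity | Needs | AUDIT (sum; used alcohol yes/no) | DAST-10 (consequences index; yes/no) |
|---|---|---|---|
| Time until first use | A start date and a date of first use | Not supplied | Not supplied |
| Number of use days | A day count over a defined window | Not supplied | Not supplied |
| Three-level status | Any use, plus the share of days with use | Approximates abstinent, alcohol only; cannot split lapse from relapse | Cannot split lapse from relapse |

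None of the 3 quantities can be fully derived. The craving scale in Subsection 2.7 does not help, because it rates craving and not use.

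**Step 3: the reverse direction.** The listed instruments carry 2 instruments × 2 codings = 4 codings labelled primary. Section 3 names none of them and gives none priority. There are two follow-up assessments, and neither is designated primary.

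**Step 4: does anything else settle the choice?** Multiple testing comes up only in the power paragraph: "Type 1 error due to multiple tests, a small-medium effect size of .3 was conservatively estimated". That explains a planning effect size. It does not rank endpoints or allocate alpha, so the question stays open.

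**The case against.** Several defences have force.

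- **Model coverage.** A reader might infer that substance use has no analysis that respects the cohort design, or only an unadjusted chi-square. The documents do not support that. Section 3 describes a mixed-effects repeated-measures approach with cohort as a random effect. The sentence on group-by-time contrasts comes directly after the TLFB sentence, so the framework can fairly be read to cover substance use. What stands is narrower: no model is tied by name to AUDIT or DAST-10, and none is specified for a censored time until first use or a three-level status.
- **Other analyses.** The structural equation models in Section 3 also include substance use and do not require the TLFB. They serve the exploratory aim, name no instrument and do not replace the primary analysis.
- **The overview table.** Its silence on the TLFB might look like further evidence. It is not: for outcomes the table lists domains, and AUDIT and DAST-10 are missing from it too.
- **Lapse timing.** One might infer that no lapse can occur before the post-assessment. Subsection 2.10 gives no interval after the seventh session. Subsection 2.2 puts the 4-month visit roughly two months after the post-assessment, which places the latter about two months after baseline. The course lasts six weeks, so a gap is possible.
- **Error rates.** A specific inflation of the false-positive rate cannot be claimed, because the plan states neither the number of confirmatory tests nor their correlations. Nor does it state a recall window from which to judge the scores.
- **Partial derivability.** The AUDIT yes/no coding does give a crude split of alcohol use. That is one level of one quantity, for one substance.

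The TLFB may in fact be collected and simply left off the lists. The documents cannot settle this, which is why the passages need reconciling.

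**Conclusion.** The point holds and must be fixed. For a primary outcome, the analysis section and the instrument lists contradict each other. None of the 3 stated quantities can be fully built from the listed instruments, and neither of the 2 listed instruments appears in Section 3. The primary substance-use analysis cannot be run as written on the listed battery, and the primary measure, coding and time point are not identified.

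This rests on the instruments as the plan describes them, and on the removed parts of the public copy holding no instrument list. By position those parts fall in the team and contact subsections. No assumption about power, correlation or recall window is needed.

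The instrument mismatch does not touch PTSD. Other list differences are a separate, minor alignment note and do not share this severity: suicidality and trauma-related guilt have no listed instrument; hopelessness and loneliness are missing from the Section 3 secondary outcomes; self-compassion and mindfulness are missing from its mediators.

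**What to change.** Before outcome data are examined, reconcile the substance-use sentence in Section 3 with Subsections 2.7 and 2.10, according to what is actually collected.

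**(a) If AUDIT and DAST-10 are collected:** replace the TLFB sentence with an analysis of both scores in the mixed-effects repeated-measures model already in Section 3, with the cohort random effect and the group-by-time contrast. Name one primary coding and time point, or split alpha between the two instruments (for example .025 each, since .025 + .025 = .05).

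**(b) If the TLFB is already collected:** add it to Subsections 2.7 and 2.10. Name one of its quantities as primary. State the start date and the window over which days are counted. Name a model that accounts for cohort and suits that quantity, such as one for a censored time until first use or for a three-level status.

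The cost is wording and a narrower primary claim. The minor list differences can be aligned in the same revision.
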